5.7. Duration of Follow Up

Participants will be followed for 12 months after removal from protocol therapy (30, 150, 250 days, and at 12 months, ± 7 -day window) or until death, whichever occurs first. Follow-up will assess for survival and progression and may be done in person or via phone/electronically. If three consecutive follow-ups are missed the patient will be considered lost to follow up and censored at the last verified date of clinical follow up (in person or electronically verified). Participants removed from protocol therapy for unacceptable adverse event(s) will be followed until resolution or stabilization of the adverse event.

5.8. Criteria for Taking a Participant Off Study

Participants will be removed from study when any of the following criteria apply:

- Lost to follow-up
- Withdrawal of consent for data submission
- Death

The reason for taking a participant off study, and the date the participant was removed, must be documented in the case report form (CRF). In addition, the study team will ensure the participant's status is updated in OnCore in accordance with [REGIST-OP-1](#).

6. DOSING DELAYS/DOSE MODIFICATIONS

MBG453 may be delayed due to toxicities. Doses may be delayed for up to 28 days for toxicity; toxicities that result in more than 28 days delay should result in discontinuation from the study medication. Patients that are deriving clinical benefit but require a treatment delay beyond 28 days for non-toxicity events should be discussed with the principal investigator.

Dosing may be resumed once an AE has resolved to baseline or to Grade 1. If a treating investigator considers it in the patient's best interest to resume therapy before resolution of an AE or to resume without dose modification this may be considered on a case-by-case basis after discussion with the overall PI of the trial.

Dose modifications of MBG453 may be accomplished through dose reduction or altering the treatment interval; provisional dose levels are shown below.

Dose delays and modifications will be made as indicated in the following table(s). The descriptions and grading scales found in the revised NCI Common Terminology Criteria for Adverse Events (CTCAE) version 5.0 will be utilized for dose delays and dose modifications. A copy of the CTCAE version 5.0 can be downloaded from the CTEP website

http://ctep.cancer.gov/protocolDevelopment/electronic_applications/ctc.htm.

Dose Level	Dose
-2	240 mg every 28 days
-1	400 mg every 28 days
0	800 mg every 28 days

If the patient experiences an AE meeting the criteria for DLT as outlined in section 5.4, including events outside the DLT period, treatment should be held. Patients may resume treatment after resolution to Grade 1 or to the patient's baseline value. If this event occurs during the first cycle (whether or not they are among the first 6 patients being evaluated for DLT assessment) a dose modification must be made. If this event occurs after the first cycle the patient may resume at the same or a lower dose at the discretion of the investigator. Specific guidance is provided below.

Infusion Reaction	Management/Next Dose for MBG453
≤ Grade 1	Decrease infusion rate until recovery
Grade 2	Stop Infusion. Before restarting, pre-medicate according to local institutional guidelines. Restart infusion at 50% of previous rate under continuous observation. Ensure that there is a minimum observation period of 1 hour prior to restarting the infusion(s). If the AE recurs at the reinitiated slow rate of infusion, and despite oral pre-medication, then discontinue treatment
Grade 3	Discontinue treatment
Grade 4	Discontinue treatment
*Participants requiring a delay of >28 days should go off protocol therapy.	
**Participants requiring > two dose reductions should go off protocol therapy.	
Recommended management: antihistamines, antipyretics, steroids, cardiopulmonary monitoring.	

GI Immune AEs	Management/Next Dose for MBG453
≤ Grade 1 (diarrhea < 4 stools/day, or asymptomatic colitis)	Continue treatment Symptomatic treatment as indicated
Grade 2 (diarrhea <4 stools/day over baseline, or colitis with pain/blood in stool)	Hold until ≤ Grade 1. Resume at same dose level. Symptomatic treatment as indicated
Grade 3 lasting > 7 days (>6 stools/d over baseline, IV fluids>24h) or colitis with medical intervention indicated	Hold* until < Grade 2. Resume at one dose level lower, if indicated.** Consider 1-2mg/kg/day methylprednisolone or equivalent Consider antibiotic treatment including prophylaxis Consider lower endoscopy
Grade 4 (life threatening)	Discontinue protocol therapy Consider 1-2mg/kg/day methylprednisolone or equivalent Consider antibiotic treatment including prophylaxis Consider lower endoscopy
*Participants requiring a delay of >28 days should go off protocol therapy.	

GI Immune AEs	Management/Next Dose for MBG453
**Participants requiring > two dose reductions should go off protocol therapy.	
Recommended management: assess for other causes, empiric corticosteroids, assessment of immune-related organ dysfunction as indicated	

Renal Immune AEs	Management/Next Dose for MBG453
≤ Grade 1 (Cr <1.5x baseline)	Continue treatment Symptomatic treatment as indicated
Grade 2-3 (Cr >1.5x baseline to 6x ULN)	Hold until ≤ Grade 1. Resume at same dose level. Symptomatic treatment as indicated Consider renal biopsy to confirm immune related Consider 0.5-1.0mg/kg/day methylprednisolone or equivalent with slow taper (>1 mo) if responds
Grade 4 (Cr > 6x ULN)	Discontinue protocol therapy Consider 1-2mg/kg/day methylprednisolone or equivalent with slow taper (>1 mo) if responds Consider nephrology input and monitor creatinine daily Consider renal biopsy
*Participants requiring a delay of >28 days should go off protocol therapy.	
**Participants requiring > two dose reductions should go off protocol therapy.	
Recommended management: assess for other causes, empiric corticosteroids, assessment of immune-related organ dysfunction as indicated	

Pulmonary Immune AEs	Management/Next Dose for MBG453
≤ Grade 1 (radiographic changes only)	Continue treatment; consider delay Symptomatic treatment as indicated, monitor every 2-3 days
Grade 2 - 3 (mild-moderate symptoms, hypoxia)	Hold until ≤ Grade 1. Resume at same dose level. Consider involving ID and pulmonary consults Monitor daily symptoms, consider hospitalization Consider bronchoscopy, lung biopsy Consider 1.0mg/kg/day methylprednisolone or equivalent with slow taper (>1 mo) if responds
Grade 4 (life threatening)	Discontinue protocol therapy Consider 2-4mg/kg/day methylprednisolone or equivalent with slow taper (at least 6 weeks) if responds Hospitalization, involvement of pulmonary and/or ID Consider antibiotic treatment including prophylaxis Consider bronchoscopy, lung biopsy
*Participants requiring a delay of >28 days should go off protocol therapy.	
**Participants requiring > two dose reductions should go off protocol therapy.	
Recommended management: assess for other causes, empiric corticosteroids, assessment of immune-related organ dysfunction as indicated	

Hepatic Immune AEs	Management/Next Dose for MBG453
≤ Grade 1 (AST/ALT ULN - 3.0x ULN and/or Tbili ULN – 2 x ULN)	Continue treatment Symptomatic treatment as indicated
Grade 2 (AST/ALT 3-5x ULN and/or Tbili 2-3x ULN)	Hold until ≤ Grade 1. Resume at same dose level. Increase monitoring frequency Symptomatic treatment as indicated
Grade 3 lasting < 7 days (AST/ALT >5-8x ULN and/or Tbili 3-5x ULN)	Hold* until < Grade 2. Resume at one dose level lower, if indicated.** Consider 1-2mg/kg/day methylprednisolone or equivalent Consider antibiotic treatment including prophylaxis Consider liver biopsy and gastroenterology consult
Grade 3 lasting > 7 days Grade 4 (AST or ALT >8x ULN and/or Tbili > 5x ULN)	Discontinue protocol therapy Consider 2mg/kg/day methylprednisolone or equivalent Consider antibiotic treatment including prophylaxis Consider liver biopsy and gastroenterology consult
*Participants requiring a delay of >28 days should go off protocol therapy.	
**Grade 3 hepatic imAEs that do not improve within 7 days on steroids should come off protocol therapy. Consideration should be given for additional immunosuppression e.g. mycophenolate mofetil 1gm BID. Participants requiring > two dose reductions should go off protocol therapy.	
Recommended management: assess for other causes, empiric corticosteroids, assessment of immune-related organ dysfunction as indicated	

Skin Immune AEs	Management/Next Dose for MBG453
≤ Grade 1-2 (<30% BSA)	Continue treatment Symptomatic treatment as indicated (antihistamines, topical steroids) If persists or recurs consider delay in therapy, consider 0.5- 1.0mg/kg/d methylprednisolone or equivalent
Grade 3-4 (>30% BSA or with life threatening consequences)	Delay or discontinue protocol therapy Consider skin biopsy Consider dermatology involvement Consider 1.0-2.0mg/kg/day methylprednisolone or equivalent with slow taper (>1 mo) if responds
SJS/TEN	Discontinue protocol therapy Consider 1-2mg/kg/day methylprednisolone or equivalent with slow taper (>1 mo) if responds Consider dermatology involvement, skin biopsy
*Participants requiring a delay of >28 days should go off protocol therapy.	
**Participants requiring > two dose reductions should go off protocol therapy.	
Recommended management: assess for other causes, empiric corticosteroids, assessment of immune-related organ dysfunction as indicated	

Neurological Immune AEs	Management/Next Dose for MBG453
≤ Grade 1 (asymptomatic/mild)	Continue treatment Symptomatic treatment as indicated
Grade 2 (Moderate, limiting iADLs)	Hold until ≤ Grade 1. Resume at same dose level. Symptomatic treatment as indicated Consider neurology involvement Consider 0.5-1.0mg/kg/day methylprednisolone or equivalent
Grade 3-4 (Cr > 6x ULN)	Delay and dose reduce (for fully reversible grade 3) or discontinue protocol therapy Consider 1-2mg/kg/day methylprednisolone or equivalent with slow taper (>1 mo) if responds Consider neurology consult and additional immunosuppressive therapies as indicated
*Participants requiring a delay of >28 days should go off protocol therapy. **Participants requiring > two dose reductions should go off protocol therapy.	
Recommended management: assess for other causes, empiric corticosteroids, assessment of immune-related organ dysfunction as indicated	

Endocrine Immune AEs	Management/Next Dose for MBG453
TSH elevation (asymptomatic)	Continue treatment Symptomatic treatment as indicated, consider endocrinology
Symptomatic endocrinopathy	Evaluate for endocrine function Consider endocrinology consult Consider pituitary imaging If symptomatic, delay in treatment and 1-2mg/kg/day methylprednisolone or equivalent with slow taper (>1 mo) if responds Appropriate hormone replacement therapy
Adrenal crisis	Delay or discontinue protocol therapy Evaluate for sepsis IV fluids, stress dose IV steroids with mineralocorticoid activity Consider endocrinology consult
*Participants requiring a delay of >28 days should go off protocol therapy. **Participants requiring > two dose reductions should go off protocol therapy.	
Recommended management: assess for other causes, empiric corticosteroids, assessment of immune-related organ dysfunction as indicated	

Other Immune-Related Toxicities	Management/Next Dose for MBG453
≤ Grade 1	Continue treatment
Grade 2	Hold until ≤ Grade 1. Resume at same dose level.
Grade 3 lasting < 7 days	Hold* until < Grade 2. Resume at one dose level lower, if indicated.**
Grade 3 lasting > 7 days	Discontinue protocol therapy

Other Immune-Related Toxicities	Management/Next Dose for MBG453
Grade 4	
*Participants requiring a delay of >28 days should go off protocol therapy. **Grade 3 imAEs that do not improve within 7 days on steroids should come off protocol therapy. Consideration should be given for additional immunosuppression. Participants requiring > two dose reductions should go off protocol therapy.	
Recommended management: assess for other causes, empiric corticosteroids, assessment of immune-related organ dysfunction as indicated (e.g. thyroid testing, pituitary testing, GI/pulmonary evaluation, neurological assessment).	

Non-Hematologic Toxicities	Management/Next Dose for MBG453
≤ Grade 1	No change in dose
Grade 2	Hold until ≤ Grade 1. Resume at same dose level.
Grade 3	Hold* until < Grade 2. Resume at one dose level lower, if indicated.**
Grade 4	Off protocol therapy
*Participants requiring a delay of >28 days should go off protocol therapy. **Participants requiring > two dose reductions should go off protocol therapy.	
Recommended management: assess for other underlying/secondary causes	

Hematologic Toxicities	Management/Next Dose for MBG453
≤ Grade 1	No change in dose
Grade 2	No change in dose
Grade 3	Hold* until < Grade 2 (or baseline if baseline was grade 2). If persistent cytopenia beyond day 42 of the cycle, or as indicated, evaluate with a bone marrow biopsy. Resume at one dose level lower, if indicated.**
Grade 4	Hold* until < Grade 2 (or baseline if baseline was grade 2). If persistent cytopenia beyond day 42 of the cycle, or as clinically indicated, evaluate with a bone marrow biopsy. If no evidence of MDS, discontinue therapy.
*Participants requiring a delay of >28 days should go off protocol therapy. **Participants requiring > two dose reductions should go off protocol therapy.	

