5.3.2. Other Modality(ies) or Procedures

N/A.

5.4. **Definition of Dose-Limiting Toxicity (DLT)**

This phase II study will include a safety lead-in to ensure there is no excess toxicity in this patient subgroup. The study will collect adverse events during the first cycle (initial 28 days) of treatment for the first 6 patients treated on study to assess for dose-limiting toxicities (DLTs). If more than one of the first six patients enrolled experiences a DLT, enrollment will pause and safety will be assessed for the lower-risk MDS population prior to further enrollment. At that point any further enrollment would depend upon discussions with the sponsor and treating investigators regarding the event, and whether to stop the study or consider amending the protocol to explore lower doses and alternative dose schedules.

DLTs should be possibly, probably, or definitely related to the study drug. The following AEs will be defined as dose-limiting toxicities if considered to be related to MBG453:

Non-hematologic toxicities:

- Grade 3 non-hematologic toxicities unless attributable to persistent MDS or CMML and excluding toxicities secondary to cytopenias (e.g. febrile neutropenia, infection due to MDS-associated neutropenia, bleeding due to thrombocytopenia).
 - The following will *not* be considered DLTs:
 - Grade 3 fatigue, asthenia, fever, anorexia, or constipation.
 - Grade 3 nausea, vomiting or diarrhea not requiring tube feeding, total parenteral nutrition, or requiring or prolonging hospitalization, and that resolve to grade 1 with appropriate treatment within 7 days
 - Grade 3 or 4 tumor lysis syndrome (TLS) if it is successfully managed clinically and resolves within 72 hours without end-organ damage. Grade 4 TLS lasting >72 hours is a DLT.
 - Grade 3 or 4 isolated electrolyte abnormalities that last < 72 hours.
- All Grade 4 non-hematologic toxicities (excluding toxicities attributable to neutropenia and thrombocytopenia due to active MDS or CMML). Conversely, complications of cytopenias including febrile neutropenia, bleeding, and infections, will be considered DLTs in the absence of evidence of active disease, as well as if the baseline for a given cell line (neutrophils, platelets) is above the threshold where such events would be expected due to disease alone.
- CTCAE grade ≥ 3 immune-related adverse events persisting > 7 days after treatment with corticosteroids (if it improves to < grade 3 it is not considered a DLT)

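### Section 6 requires a dose modification after a cycle 1 DLT, but several of the table rows it points to say to resume at the same dose level

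*Combined protocol and SAP*

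**What the plan says.** The general text of section 6 covers any event meeting the DLT criteria of section 5.4.

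- **In cycle 1**, for every patient and not only the first six: "patients being evaluated for DLT assessment) a dose modification must be made".
- **After cycle 1**: "the patient may resume at the same or a lower dose at the discretion of the investigator".
- **What counts as a modification**: "Dose modifications of MBG453 may be accomplished through dose reduction or altering the treatment interval; provisional dose levels are shown below". The three levels listed are 800, 400 and 240 mg, each every 28 days.
- **Departures**: an investigator who thinks it best for the patient may ask to "resume without dose modification this may be considered on a case-by-case basis after discussion with the overall PI of the trial".
- **Status of the tables**: the section says that delays and modifications follow the tables, and closes the DLT paragraph with "Specific guidance is provided below".

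The tables then give these instructions:

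- Renal immune events, grade 2-3: "Hold until ≤ Grade 1. Resume at same dose level. Symptomatic treatment as indicated Consider renal biopsy to confirm immune related".
- Pulmonary immune events, grade 2-3: "Hold until ≤ Grade 1. Resume at same dose level. Consider involving ID and pulmonary consults".
- Grade 2 rows of the 'Other Immune-Related' and 'Non-Hematologic' tables: hold until grade 1 or better, then the same dose level.
- A footnote under the 'Other Immune-Related' table takes grade 3 immune events off treatment if a week of steroids brings no improvement. The hepatic table has its own version, limited to hepatic events. The renal and pulmonary tables have none.

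Two DLT criteria in section 5.4 matter here. One is "CTCAE grade ≥ 3 immune-related adverse events persisting > 7 days after treatment with corticosteroids", with the proviso that improvement below grade 3 means the event is not a DLT. The other covers eye pain or loss of visual acuity of grade 2 or worse that fails to reach grade 1 after two weeks of topical therapy, or that needs systemic treatment.

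**The concern.** This is the rule for giving the drug again after a dose-limiting toxicity. For the same patient, the general text requires a change of dose or interval, while the row for that organ and grade says to change neither. Both are written as instructions, and the general text itself names the tables as the specific guidance. A site that follows the paragraph lowers the dose or lengthens the interval. A site that follows the row repeats 800 mg every 28 days, which is 800 / 400 = 2 times the dose at level -1. What is at stake is the safety of the individual patient and consistency between sites.

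**Working it through.** The plan states no figure to reproduce, so the check is mainly a comparison of texts.

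**Step 1. Which cycle 1 DLTs fall in a row that says same dose level?**

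| Event in cycle 1, related to MBG453 | DLT under 5.4? | General text of section 6 | Table row |
|---|---|---|---|
| Grade 3 renal immune event, more than 7 days on steroids | Yes | Modify | Same level |
| Grade 3 pulmonary immune event, more than 7 days on steroids | Yes | Modify | Same level |
| Grade 2 eye event meeting the eye criterion, judged immune-related | Yes | Modify | Same level ('Other' grade 2) |
| Grade 2 eye event meeting the eye criterion, not judged immune-related | Yes | Modify | Same level ('Non-Hematologic' grade 2) |
| Grade 3 renal or pulmonary immune event that improves below grade 3 on steroids in time | No | No cycle 1 requirement | Same level; no conflict |
| Any of these DLTs after cycle 1 | Yes | Same or lower dose | Same level; no conflict |

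**Step 2. Can 'same dose level' still be a modification?** No. An altered interval counts as a modification, but level 0 is defined by both dose and interval (800 mg every 28 days). Keeping the level keeps both.

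**Step 3. Can such a patient be re-dosed at all?** Dose 2 is due on day 1 + 28 = 29. A delay of up to 28 days allows it until day 29 + 28 = 57, so re-dosing is possible in principle. The renal and pulmonary rows suggest a steroid taper of more than a month, and section 5.2.2 requires no more than 10 mg/day of prednisone before the next dose, so some patients would pass the delay limit and stop treatment. The documents do not give recovery or taper times, so no window of onset days is claimed.

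**Step 4. Does the footnote settle it?** Its wording is not limited to an organ, but it stands under the 'Other' table. If it reaches renal and pulmonary events, the patient with a steroid-persistent grade 3 event has three instructions: modify, same level, discontinue. If it does not, there are two. For grade 2 eye events it is not relevant.

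**Step 5. How often?** Inputs from sections 2.2 and 7.1.4:

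- Single-agent patients: 133 (solid tumors) + 26 (MDS/AML) = 159. Renal or pulmonary immune events listed: 0.
- One-sided 95% upper bound for 0 of n: 1 - 0.05^(1/n) = 1 - 0.05^(1/159) = 0.0187, or 1.9%, for any grade.
- At that bound, 22 patients would give 22 x 0.0187 = 0.41 expected events of any grade. The subset that triggers the conflict is smaller, and the documents give no rate for it or for the eye criterion.
- Combination patients: (252 - 133) + (152 - 26) = 119 + 126 = 245. One renal immune event is listed, a grade 3 tubulointerstitial nephritis reported as a DLT within the first 2 cycles, with PDR001 and decitabine. A grade 2 uveitis was also reported as a DLT, on the same three-drug combination.

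**The case against.** The strongest reply is that the texts can be read in harmony. The mandatory sentence is the narrower one, since it applies only to cycle 1 DLTs. The rows cover all cycles and mention neither DLT status nor cycle. Departures from modification go to the overall PI, which suggests that modification is the default. This is a sensible reading and probably the intended one. But it is stated nowhere. The rows are also specific in their own way, by organ and grade, and the text calls them the specific guidance. The route through the overall PI is a case-by-case exception, whereas the rows set a default and mention no discussion.

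A second reply is that the event is very rare and no trial result depends on it. That stands, and it is why the point is minor.

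A reader might infer more than the documents support:

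- *That section 6 contradicts itself throughout.* It does not. The rows that give one level lower if indicated leave room for the required modification, and several severe-event rows already call for reduction or discontinuation.
- *That every grade 2 event, or every grade 3 renal or pulmonary event, is affected.* Only those that meet a section 5.4 criterion in cycle 1 are.
- *That the nephritis and uveitis cases show the risk with MBG453 alone.* Both occurred with PDR001 and decitabine, and section 7.1.4 says that attribution to TIM-3 inhibition alone is unclear.
- *That the creatinine label on the neurological grade 3-4 row (above six times the upper limit of normal, the same as the renal grade 4 row) leads to wrong dosing.* It looks like a copying error. Section 6 requires CTCAE v5.0 grading, and the row's actions are neurological, so it is an editorial matter.

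**Conclusion.** The conflict is present in the current text and should be corrected. It is minor and concerns patient safety. It affects a related grade 3 renal or pulmonary immune event persisting more than 7 days on corticosteroids, and a grade 2 eye event meeting the DLT criterion, when either occurs in cycle 1 and the patient recovers in time to be re-dosed. Whether the discontinuation footnote also applies to the renal and pulmonary cases is unclear.

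The 1.9% bound assumes that an event not listed did not occur and that the earlier single-agent patients resemble those in this trial. It covers renal and pulmonary immune events of any grade, not the triggering subset and not eye events.

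A reader might also infer that the efficacy result or the six-patient safety rule is compromised. It is not. The response rate, the two-stage boundaries, the sample size and the error rates do not use the re-dosing rule, and the safety rule counts DLTs whatever dose follows.

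**What to change.** Add one sentence to the DLT paragraph of section 6, for example: *For a cycle 1 event meeting DLT criteria, the dose-modification requirement (dose reduction or longer interval) overrides any same-dose-level entry in the tables below; where a table or its footnote requires discontinuation, discontinue.* The rows themselves can stay as they are, so that events that are not DLTs keep their present rule. The case-by-case route through the overall PI need not change.

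State also whether the footnote on steroid-persistent grade 3 immune events applies to renal and pulmonary events. If it does not, these patients may be re-dosed at a modified regimen while the corresponding hepatic events are discontinued. That should be a deliberate choice.

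As an editorial correction, relabel the neurological grade 3-4 row as severe or life-threatening, per CTCAE v5.0.

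The cost is a wording amendment: no extra patients, visits or procedures. The downside is lower or less frequent dosing in rare patients, or loss of treatment for some if the footnote is declared to apply.

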5. TREATMENT PLAN

5.1. Treatment Regimen

We will plan to treat patients with MBG453 on day 1 of a 28-day cycle. Patients will be treated with MBG453 dosed at 800mg every 28 days. AEs will be assessed, with particular attention paid to monitoring for immune mediated adverse events. The primary endpoint, ORR, will be assessed as the best response during the first 6 months of treatment. Patients may stay on treatment until progression. The study will assume a historical null response rate of 0.15 (e.g. based on MEDALIST) and will be powered to detect an ORR of 0.35 with MBG453.

MBG453 will be administered on day 1 of each cycle, where 28 consecutive days is defined as a treatment cycle. Treatment will be administered on an outpatient basis. Reported adverse events and potential risks are described in Section 7. Appropriate dose modifications are described in Section 6. No investigational or commercial agents or therapies other than those described below may be administered with the intent to treat the participant's malignancy.

Patients should not receive pre-medication to prevent infusion reactions before the first infusion of MBG453, in order to determine if pre-medication is necessary. If a patient experiences an infusion reaction he/she may receive pre-medication on subsequent dosing days. The pre-medication should be chosen per institutional standard of care, at the discretion of the treating investigator. Acute allergic reactions should be treated as per institutional standard of care. In the event of anaphylactic/anaphylactoid reactions, this includes any therapy necessary to restore normal cardiopulmonary status. If a patient experiences a Grade 3 anaphylactic/anaphylactoid reaction, the patient will be discontinued from the study. Patients should be treated at a facility equipped for cardiopulmonary resuscitation. Appropriate resuscitation equipment should be available at the bedside and a physician readily available.

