- CTCAE grade ≥ 2 eye pain or reduction of visual acuity that does not respond to topical therapy and does not improve to grade 1 severity within 2 weeks of initiating topical therapy or requiring systemic treatment

- Treatment-related deaths

Hematologic toxicities:

- \geq Grade 3 hematologic toxicities attributed to active MDS will not be considered DLTs, including complications attributed to cytopenias from disease such as infections during neutropenia or bleeding events during thrombocytopenia. As above this does not include such events in the absence of disease or if occurring at a baseline cell count where such events would be expected.
- Grade 4 neutropenia or thrombocytopenia lasting more than 14 days, and associated with a marrow absent features of MDS, is considered a DLT. A bone marrow assessment is recommended if there is suspicion of drug-related cytopenias.
- In the setting of new grade 4 cytopenias thought possibly, probably, or definitely related, and not resolving to grade 3 or better within 14 days, a bone marrow is recommended. If the bone marrow is absent of disease then this would be considered a DLT.

Management and dose modifications associated with the above adverse events are outlined in Section 6.

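### The GI immune-toxicity table prints a grade 2 (hold) diarrhea limit that overlaps grade 1 (continue) and leaves 4 to 6 extra stools in no stool-count row

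*Combined protocol and SAP*

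**What the plan says.** Section 5.1 sends sites to Section 6 for dosing changes: "Appropriate dose modifications are described in Section 6". Section 6 makes its tables directive: "Dose delays and modifications will be made as indicated in the following table(s". It also says that CTCAE "version 5.0 will be utilized for dose delays and dose modifications".

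The GI Immune AEs table has three rows with a stool count:

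- Continue treatment: "≤ Grade 1 (diarrhea < 4 stools/day, or asymptomatic colitis".
- Hold until the event is back to grade 1 or lower, then resume at the same dose: "Grade 2 (diarrhea <4 stools/day over baseline, or colitis with pain/blood in stool".
- Hold until below grade 2, then resume one dose level lower if indicated: "Grade 3 lasting > 7 days (>6 stools/d over baseline, IV fluids>24h) or colitis with medical intervention indicated".

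The grade 4 row is defined by life-threatening severity and has no stool count.

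Two later tables in Section 6, Other Immune-Related Toxicities and Non-Hematologic Toxicities, are organized by grade without stool counts. Both hold a grade 2 event until it is grade 1 or lower and then resume at the same dose.

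**The concern.** Rows that call for different actions should not overlap, and together they should cover every case. Here the limits for continue and for hold have the same number and the same direction, while the next row starts at a much higher count. The grade 1 row also leaves out the reference to baseline that the other two rows carry.

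At stake is a hold threshold for an immune checkpoint antibody. A site working from the bracketed stool counts could continue or hold the same patient, and would find no count to match a patient with 4 to 6 extra stools. The release point is blurred too, because a grade 2 hold ends on return to grade 1, and the two descriptors overlap. Nothing in the response endpoint, the two-stage rule or the sample size depends on this table.

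**Working it through.** The plan has no calculated figure to reproduce here. The check applies the printed limits to whole stool counts.

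**Inputs (Section 6, GI Immune AEs).** Let B be the patient's usual stools per day (B ≥ 0), T the total per day during the event, and I = T − B the increase over baseline.

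- Grade 1 row (continue): T < 4.
- Grade 2 row (hold): I < 4.
- Grade 3 row (hold, lower dose if indicated): I > 6, lasting more than 7 days.

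**Step 1, overlap.** Since B ≥ 0, I = T − B ≤ T. So T < 4 always implies I < 4. Example: B = 1, T = 3 gives I = 2. Both the continue row and the hold row apply, whatever the baseline.

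**Step 2, gap.** Take I = 4, 5 or 6. I < 4 is false and I > 6 is false. T = B + I is at least 4, so T < 4 is false as well. Example: B = 1, I = 5 gives T = 6 and no stool-count row. Such a patient could still enter the grade 2 row through its colitis criterion; the gap concerns the count only.

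**Step 3, mixed reference.** Grade 1 uses an absolute total and grades 2 and 3 use an increase. With B = 3 and T = 5, I = 2. Grade 1 fails (5 is not below 4) and grade 2 is met, so a rise of only 2 stools falls in the hold row alone. If grade 1 were also stated over baseline, I = 2 would meet it.

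**Step 4, duration.** The grade 3 stool count is tied to events lasting more than 7 days. An increase of 7 or more that lasts 7 days or less meets no GI stool-count row. The Non-Hematologic table holds grade 3 events of any duration, and the Other Immune-Related table holds those lasting less than 7 days, so an action exists elsewhere.

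**Step 5, the correction.** The adjacent limits determine it. With all rows over baseline, grade 1 as I < 4, grade 2 as I = 4 to 6 and grade 3 as I > 6 split whole counts into 0–3, 4–6, and 7 or more, with no overlap and no gap in the counts. An open-ended grade 2 limit of 4 or more would not do this: I = 7 satisfies both 7 ≥ 4 and 7 > 6.

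**The case against.** The best reply is that the grade, not the bracketed count, selects the row. Every row is headed by a grade, and Section 6 applies CTCAE version 5.0 to dose delays and modifications. A site that grades first and then reads the action will hold a grade 2 event, and both general tables give the same action. This largely stands, and it is why the point is minor. It does not remove the error. The CTCAE stool limits are not printed in the documents, the protocol prints its own, and Section 6 does not say which prevails if they differ.

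A second reply is that a ≥ sign was turned into < when the PDF was converted to text. That is unlikely but not excluded. The ≤ sign is intact in this same table, and ≥ is intact in Section 5.4: "CTCAE grade ≥ 2 eye pain or reduction of visual acuity that does not respond to topical therapy". On the other side, no ≥ appears in the Section 6 tables for comparison, and one bullet in Section 5.4 shows the symbol as a raw code. The source PDF should settle it.

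A reader might infer three stronger things, none of which the documents support:

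- *That patients with 4 to 6 extra stools have no instruction at all.* They have no GI stool-count row, but once the event is graded 2 the action is to hold.
- *That the number misdosed can be estimated.* Section 2.2 reports diarrhea in 5 of 26 patients on single-agent MBG453, but for any grade and any cause. Section 7.1.4 lists no GI event among the possible immune-mediated events with the single agent. The documents do not give the share with 4 to 6 extra stools.
- *That the GI table is wrong to allow resumption after grade 3 lasting more than 7 days, because the hepatic table discontinues.* Organ-specific tables may differ; that is a clinical choice.

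**Conclusion.** The printed grade 2 diarrhea limit is inconsistent with the rows on either side. A daily total below 4 meets two opposite actions, and an increase of 4, 5 or 6 over baseline meets no stool-count row. This rests on reading the bracketed limits as printed, on whole stool counts, and on the < sign being in the source PDF.

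The size is small. CTCAE grading and the grade 2 hold in the two general tables lead to the right action when the site grades first. How many patients could be affected cannot be derived from the documents. Design, sample size, error rates and analysis are untouched. It should still be corrected, because the tables direct dosing and the change is almost free.

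A separate drafting slip in the same set of tables belongs in the same amendment. The neurological row reads "Grade 3-4 (Cr > 6x ULN", which is the creatinine limit of the renal grade 4 row. It does not prove that the diarrhea limit is in the source, but it needs correcting whatever the PDF shows.

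**What to change.** First check the GI grade 2 limit against the source PDF. Then, in one amendment to Section 6:

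1. GI grade 1: fewer than 4 stools a day over baseline.
2. GI grade 2: 4 to 6 stools a day over baseline. Use this closed range even if the PDF turns out to read ≥4, because an open-ended limit overlaps the row for more than 6.
3. GI grade 3: add a cross-reference to the Other Immune-Related and Non-Hematologic tables for grade 3 diarrhea lasting 7 days or less. Limit it to those events. For exactly 7 days, point to the Non-Hematologic table, since the other table speaks only of less than or more than 7.
4. Neurological grade 3-4: replace the creatinine limit with a neurological descriptor chosen by the clinical team.

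The cost is two table entries, one cross-reference and one row descriptor. Visits, sample size and analysis do not change.
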